Headache Long Term Follow-up in Patients Who Suffered From PTCS

During Their Childhood

1.7.24

PI [name]

ERB # BNZ 72-21

1. Introduction

Pseudotumor Cerebri (PTC) is an uncommon syndrome characterized by increased intracranial pressure due to an unclear (idiopathic) cause, leading to pressure on the optic nerve and headaches. The diagnostic criteria include signs of increased pressure: headaches and vomiting, optic disc swelling (papilledema) observed in eye examinations, normal brain imaging, and elevated opening pressure in lumbar puncture with normal CSF fluid content.

The prevalence of the syndrome in the general population is approximately 1 in 100,000. The syndrome can occur at any age, including in children, where the incidence varies across different studies from 26% to 85%. In women of childbearing age, the prevalence increases to approximately 3.5 per 100,000. Among women whose weight exceeds the ideal body weight, the prevalence reaches 19 per 100,000, which is 19 times higher in obese women of childbearing age.

In prepubescent children, most patients are young, thin boys. The most common symptom of PTC in adults (occurring in 90% of cases) is headache. Another symptom is transient vision loss, ranging from mild blurring to complete loss of vision, which may accompany headaches or occur independently. Among the pediatric population, symptoms vary by age: older children and adolescents typically complain of headaches accompanied by vomiting, similar to adults, while younger children may present with irritability, diplopia, strabismus, and stiff neck, and may even be asymptomatic. In infants, the only symptom might be sleepiness or apathy. In all patients, there is some evidence of optic nerve disease, such as slightly reduced visual acuity, color deficiency, or visual field defects.

The prognosis concerning optic nerve damage is good. Studies have shown that only 3-4% suffered from mild vision impairment, and severe impairment was extremely rare. But what about headaches? Short-term studies (3 months) have shown that about 70% will stop complaining of headaches, with an apparent link between the initial presentation and the final outcome.

The goal of this study is to examine how many will continue to suffer from headaches 10 years after the initial diagnosis, what factors predict these complaints, and whether and how it is possible to intervene to improve this outcome.

2. Research Hypothesis

A significant portion of patients diagnosed with PTC during childhood will continue to suffer from headaches despite the resolution of elevated intracranial pressure.

3. Research Methods

The study will be conducted prospectively, utilizing existing medical records of patients previously diagnosed with PTC. Patients diagnosed with PTC who were under follow-up in the pediatric neurology clinics at the following centers: Bnai Zion, Ruth-Rappaport Rambam, Hadassah Jerusalem, Schneider Petah Tikva, Dana Tel Aviv, and Hillel Yaffe Hadera, will be contacted by phone. After obtaining informed consent, a telephone interview will be

conducted, gathering information about headaches and quality of life. Information regarding PTC will be extracted from the medical records. We will use a demographic questionnaire to assess the type of headaches, the HIT-6 questionnaire to evaluate headache severity, and a validated quality of life questionnaire.

Inclusion Criteria: Patients who were diagnosed with PTC in childhood according to accepted criteria, have diagnostic information available in their records, are willing to participate in the study, and complete the questionnaires over the phone.

Exclusion Criteria: Patients who refuse to answer the questionnaire, or those without details of their initial diagnosis or follow-up in the medical records.

4. Variables

The variables in the study will include the current status and nature of the headaches and quality of life, compared to the demographic, clinical, and laboratory measures at the time of their original diagnosis.

The initial diagnosis of PTC will be extracted from the records, including:

- Age, gender, height, and weight (BMI)
- Initial presentation, with emphasis on the duration of headaches before diagnosis
- Eye examination findings, including fundus examination

5. Statistics

Data analysis will be conducted using statistical tools in SPSS. The analysis will allow for the characterization of the patient population and the examination of the relationships between the various demographic, clinical, and laboratory parameters studied, as well as their mutual influence. Statistical significance will be determined with a p-value of less than 0.05.

6. Ethical Considerations

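### Current headache in former patients is read as headache that continues after PTC, but with no reference level the data cannot separate a sequel of PTC from ordinary headache

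*Protocol*

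**What the plan says.** Protocol section 2 (Research Hypothesis) states: "A significant portion of patients diagnosed with PTC during childhood will continue to suffer from headaches", even though the raised intracranial pressure has resolved. The goal at the end of section 1 (Introduction) is to "examine how many will continue to suffer from headaches 10 years after the initial diagnosis", to learn "what factors predict these complaints", and to ask whether the outcome can be improved by intervention.

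Section 4 (Variables) states: "The variables in the study will include the current status and nature of the headaches and quality of life". These are to be set against measures taken when PTC was first diagnosed. Section 3 (Research Methods) names the instruments: "We will use a demographic questionnaire to assess the type of headaches, the HIT-6 questionnaire to evaluate headache severity", plus a quality of life questionnaire. No score, frequency, headache type or recall period says who counts as still suffering.

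The study population in section 3 is "Patients who were diagnosed with PTC in childhood according to accepted criteria, have diagnostic information available in their records", with consent and completed questionnaires. Nobody without a PTC history is enrolled, and no population figure is named. The only comparison is with the patients' own measures at diagnosis. Those listed include age, gender, BMI, eye findings and how long headaches had lasted by the time of diagnosis. Primary headache preceding PTC and family migraine are not listed.

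The one headache rate in the document is in section 1: about 70% headache-free at 3 months in earlier studies. It is given as background and not used as a benchmark. The 0.05 level in section 5 (Statistics) is not linked to a test of the hypothesis.

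**The concern.** The hypothesis is about persistence: headache that goes on although the pressure has resolved. What is measured is a non-specific symptom, about ten years later, in people whom section 6 describes as young or adult. Some of them would have headache now had they never had PTC. Persistence can be inferred only by knowing roughly how many, or by a history that links today's headache to the illness. The plan as written secures neither.

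Restricting the analysis to patients who had headache at diagnosis would not solve this, because they too are exposed to ordinary headache.

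Two conclusions are at stake. A sizeable proportion could be presented as the long-term legacy of childhood PTC when part or all of it is background. And if age or sex is related to headache generally, that relation could be described as PTC prognosis and carried into the question of whom to treat.

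**Working it through.** The Protocol states no sample size, target rate or power, so there is no figure of its own to reproduce. The calculations below are illustrations. The background rate b, the sample size n, the level L at which a share counts as significant, and the observed 50% are all assumptions.

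**1. What one observed proportion could mean.** Excess = observed share minus background share. With 50% observed:
- b = 30%: 50 - 30 = +20 points.
- b = 60%: 50 - 60 = -10 points.

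The same result fits a clear excess or none.

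**2. How often ordinary headache alone would appear to support the hypothesis.** Suppose PTC leaves no excess, so the number with headache is X ~ Binomial(n, b). The chance that the observed share reaches L is P(X ≥ L·n), rounding L·n up. For example, with n = 50 and L = 20% this is P(X ≥ 10).

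| Background b | L = 20%: n = 30 / 50 / 100 | L = 30%: n = 30 / 50 / 100 |
|---|---|---|
| 20% | 57.2 / 55.6 / 54.0% | 12.9 / 6.1 / 1.1% |
| 30% | 92.3 / 96.0 / 99.1% | 56.8 / 55.3 / 53.8% |
| 40% | 99.4 / 99.9 / 100.0% | 90.6 / 94.6 / 98.5% |
| 50% | 100.0 / 100.0 / 100.0% | 99.2 / 99.9 / 100.0% |

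A stricter reading requires the exact 95% lower limit to exceed L. For L = 20% the chances are then 15.9 / 31.6 / 62.3% at b = 30%, and 56.9 / 84.4 / 99.2% at b = 40%.

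The answer runs from about 1% to nearly 100%, depending on b and L, and the document fixes neither.

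**3. What a named reference does.** Require the exact (Clopper-Pearson) 95% lower limit to exceed b. With n = 50 the smallest qualifying counts are:
- b = 20%: 17/50 = 34%
- b = 30%: 23/50 = 46%
- b = 40%: 28/50 = 56%
- b = 50%: 33/50 = 66%
- b = 60%: 38/50 = 76%

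So 25/50 = 50% would lie above a reference of 20% or 30%, but not above 40% or more.

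Under this rule the chance of claiming an excess when there is none is 0.95% to 2.48% (n = 30 to 100, b = 20% to 60%). The chance of detecting a true 20-point excess over b = 20% to 50% is 56.9-58.9% at n = 30, 76.0-84.4% at n = 50 and 97.3-99.2% at n = 100.

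**The case against.** The strongest reply is that this is a descriptive follow-up study. A prevalence goal needs no null value, and the Protocol never states that PTC causes the present headache. The HIT-6 cut-off is a detail that a statistical analysis plan, not shown here, could properly supply. The magnitudes rest on assumed inputs, and a well-matched published reference may not exist.

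Much of this stands, and it rules out several stronger readings that a reader might infer:

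- **That any headache, however trivial, counts as a case.** The text does not say so. Headache type and HIT-6 are collected, and those data can tell an occasional mild headache from a disabling one. What is missing is the link to the headline proportion.
- **That the hypothesis cannot fail.** A share near zero would contradict it, and the table shows that some combinations of background and level would fail often. The supportable statement is that no failure level is fixed.
- **That prior and family headache are not asked about.** The questionnaire items are not shown. One can say only that these items are not among the listed variables, and that the duration of headache at diagnosis does not clearly separate earlier primary headache from the onset of PTC.
- **That age and sex results would be spurious.** They can validly predict headache within this cohort. The problem arises only if they are read as specific to PTC.

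What the reply does not meet is the wording of the hypothesis. To say that headache continues after the pressure has resolved goes beyond prevalence. An analysis plan could add a cut-off, but it could not recover history that the telephone interview did not ask for.

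**Conclusion.** The point holds as a limit on inference. The plan can estimate how common headache is in former PTC patients. As written, it cannot show that this headache is a continuation of PTC, because it has no comparison group or external reference and fixes no level for the share it predicts.

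The size cannot be settled from the documents. On an assumed background of 30% to 60%, an observed 50% spans +20 to -10 points of excess. With the significant share read as 20% and a background of 30%, ordinary headache alone would reach it 92% to 99% of the time. At a 20% background that falls to 54% to 57%, and to 1% to 13% if the share is read as 30%. This dependence on an unstated background is the reason to name a reference. The matter should be put right before the interviews; it does not invalidate the study.

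**What to change.** Before the calls begin:

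1. Define the headline outcome by a pre-set HIT-6 category, with any current headache as a secondary figure.
2. Name a published general-population figure, specific to age and sex, with as close a definition as is available. Report the observed proportion with its 95% confidence interval beside it, and state any mismatch of definition.
3. Confirm that the interview asks about recurrent headache before PTC and about family migraine; add the items if it does not.
4. Word the hypothesis and conclusion as prevalence in former patients, unless the interval lies above the reference.
5. Describe age and sex as predictors within this cohort, not as PTC-specific factors.

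The cost is at most a few interview questions, one reference table and more cautious wording. HIT-6 is already planned and no control group is needed. The downsides are a lower headline proportion than any headache would give, an imperfectly matched reference, and limited ability to show an excess if the cohort is small (under 60% for a 20-point excess at an assumed n of 30).

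### The hypothesis concerns headache after raised intracranial pressure has resolved, but no named record item, interview topic or eligibility criterion establishes whether PTC resolved or recurred

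*Protocol*

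**What the plan says.** The Introduction of the protocol sets three aims: how many patients still have headache ten years on from diagnosis, what predicts it, and whether intervention could help. Section 2 narrows this to a hypothesis with a condition attached: "A significant portion of patients diagnosed with PTC during childhood will continue to suffer from headaches despite the resolution of elevated intracranial pressure".

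Section 3 gives two data sources. The first is a telephone interview, to be "conducted, gathering information about headaches and quality of life". Its instruments are described in these words: "We will use a demographic questionnaire to assess the type of headaches, the HIT-6 questionnaire to evaluate headache severity", together with a quality of life instrument. The second is the chart: "Information regarding PTC will be extracted from the medical records".

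Section 4 says what the chart data are for. Current status is to be "compared to the demographic, clinical, and laboratory measures at the time of their original diagnosis". It then itemises: "The initial diagnosis of PTC will be extracted from the records, including" demographics with BMI, the initial presentation with headache duration, and eye findings with the fundus.

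Patients are those "who were under follow-up in the pediatric neurology clinics at the following centers", six of which are listed. Among those excluded are "those without details of their initial diagnosis or follow-up in the medical records".

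**The concern.** The hypothesis needs three facts about each patient: PTC in childhood, headache now, and raised pressure that has gone away. The plan names a source for the first two and none for the third. A patient whose pressure has returned, or never settled, would be counted in the same way as one whose headache outlasted the disease.

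Three conclusions are exposed:

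- **The hypothesis.** A finding of headache after resolution would rest on a condition that nobody checked.
- **The predictors.** A baseline factor that predicts recurrence could be reported as one that predicts residual headache. BMI is a named baseline variable, and the Introduction links excess weight to higher PTC prevalence in women. An association between BMI and headache would therefore be open to either reading. This is an inference: the protocol reports prevalence, not recurrence.
- **The intervention aim.** What to do about returned pressure is a different question from what to do about headache without it.

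This is not detail that can simply be left to an analysis plan. What is collected and who is eligible are protocol matters.

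**Working it through.** The protocol states no figure on this point, so there is nothing to reproduce. The check is to take each place where resolution or recurrence could be established and see whether it is.

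1. **Interview topics (Section 3).** Headache and quality of life are the two topics given. Section 6 describes the purpose of contacting the patient in the same two terms. No topic on the course of PTC is described.
2. **Questionnaires (Section 3).** One covers headache type, HIT-6 covers severity, and one covers quality of life. None is described as recording PTC status. Headache type may point towards or away from raised pressure, but it does not establish that pressure resolved.
3. **Record items (Section 4).** There are three bullets, all under the initial diagnosis. The fundus examination is one of them, so it too is a baseline finding. No follow-up fundus, repeat opening pressure, end of treatment, resolution or relapse is named. Count: 0 of 3.
4. **Record extraction in general (Section 3).** The sentence allows any PTC information to be taken but names none.
5. **Eligibility (Section 3).** Details of follow-up must exist in the chart. Their content is not specified, resolution is not required, and active or recurrent PTC is not excluded.

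Take two patients with the same baseline record, the same headache type and the same HIT-6 score, one with resolved pressure and one in relapse. On the items the plan names, they are identical.

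Next, what could be repaired later. The charts are existing documents that every eligible patient must have, so a resolution or recurrence noted in them can be abstracted at any time. What cannot be recovered that way is history the charts do not hold. That possibility is real: patients were followed in pediatric clinics, the time point of interest is ten years on, and Section 6 expects some patients to be adults when contacted. The protocol does not say how far the records run. For events after the last note, the telephone call is the natural source, and no recurrence question is described for it.

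Finally, what is unaffected. The proportion with headache at ten years, from any cause, needs no knowledge of pressure.

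**The case against.** The strongest reply is that the Section 4 list is plainly not complete. It is introduced as a list of inclusions, and Sections 4 and 5 both promise laboratory measures although no bullet is a laboratory item. Omission from such a list does not prove that an item will go uncollected. Excluding patients without follow-up details also makes little sense unless follow-up is read. The questionnaires are not reproduced, and one of them may already ask about relapse. The headline aim is untouched, and Section 5 ties no formal test to the resolution clause.

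Most of this stands, and it limits the point. A reader might infer that the study cannot separate the two kinds of headache, or that the call is confined to two topics. The documents support neither: the extraction sentence is general, and the interview description does not say that nothing else is asked. A reader might also infer that the information is lost for good if it is not collected now; that fails for anything the charts hold.

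What the reply does not supply is a named item. A permissive sentence does not make six centers record the same resolution field, and it does nothing for events after the last chart note. Recurrence is also not a remote possibility for this protocol: its own reference list includes a paper on visual outcome and recurrence rate in children with the condition.

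It is fair to add that chart judgment plus one recall question does not prove that pressure stayed normal. It does replace an unstated assumption with a documented one.

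**Conclusion.** The concern holds as a gap in specification. The hypothesis depends on resolved pressure, and no named record item, interview topic or eligibility criterion establishes it. The overall ten-year headache count remains valid. The conclusion about headache despite resolution, and the predictor analysis, could mix two different groups.

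The size is unknown. It would depend on the share of patients in recurrence and on how common headache is with and without it; the protocol gives no recurrence rate. It is tempting to build an estimate from the Introduction, which gives headache in 90% of adult PTC cases and about 70% free of headache complaints at three months. Neither figure fits. The first describes PTC in adults, not relapse after childhood disease. The second is a short-term figure that is not restricted to patients whose pressure had resolved, so it may already contain the mixing at issue. Nor do the documents give an age at which records stop, or limit extraction to pediatric notes, so the number of uncovered years cannot be stated either.

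The verdict assumes that the unseen questionnaires contain no recurrence item. If one does, the interview part is met by naming it. This is a cheap improvement worth making; it does not invalidate the study.

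**What to change.** - **Section 4:** add two fields from the follow-up records: whether raised pressure was judged resolved (yes / no / not documented), and any documented recurrence with its date.
- **Section 3:** add one question to the same call on whether a PTC recurrence has been diagnosed or treated since the original episode, and when. If an existing questionnaire already asks this, name the item instead.
- **Section 5:** report headache prevalence and predictors in all participants, and again in those with documented resolution and no reported or documented recurrence. Show the not-documented group separately so that it is not counted as resolved.
- **If the data cannot be obtained:** drop the resolution clause from the conclusion and report headache from any cause. If calls are already complete, the chart fields can still be abstracted.

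The cost is roughly a minute per call, two fields from charts that must be available anyway, and a minor amendment, perhaps with a matching change to the contact or consent wording. No visit or procedure is added. There are downsides. Recall is imperfect and an undiagnosed recurrence is still missed. The restricted set is smaller, and it also drops people whose recurrence has since resolved.
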